4.3 Justification for Dose

Emraclidine doses and dosing frequency in this trial are based on the safety/tolerability data and PK profile of emraclidine from Trials C2561001 and CVL-231-SCH-001. The targeted maximum dose level of 30 mg QD in this trial represents the top end of the therapeutic dose range for emraclidine. The emraclidine 30 mg QD dose demonstrated clinically meaningful and statistically significant antipsychotic activity compared with placebo as assessed by changes from Baseline at Week 6 in the PANSS total score in a Phase 1b trial in participants with an acute exacerbation of schizophrenia. emraclidine 30 mg QD, dosed for up to 6 weeks without titration, has been deemed safe and well tolerated in participants with schizophrenia. As mentioned above, this dose was associated with a maximum increase of 4.4 bpm in supine heart rate and 1.2 mmHg in supine systolic blood pressure (Week 6 average at 2 hours post morning dose compared with placebo).

The 15 mg QD dose is selected to understand the efficacy at a lower dose. Based on range of doses evaluated in the multiple ascending dose trial (CVL-231-SCH-001), the 15 mg QD dose is expected to be safe and well tolerated. The 2 doses of 30 mg QD and 15 mg QD will facilitate the evaluation of efficacy of emraclidine across a wide exposure range for a thorough understanding of exposure responsiveness of emraclidine effects.

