### **5.9.2. Main Analytical Approach**

The change from baseline to each study visit in total PANSS score will be summarized by visit and treatment group. A MMRM analysis will be used to analyze the data from all post-randomization timepoints up to Week 6 with treatment, geographic region, visit, and treatment by visit interaction as fixed effect, subject as a random effect, and baseline PANSS score as a covariate. An unstructured covariance structure will be used for the repeated measures. If the unstructured covariance matrix results in convergence issue, the heterogeneous Toeplitz covariance structure followed by the heterogeneous first-order autoregressive (AR(1)) structure will be used. The Kenward-Roger approximation will be used to estimate the denominator degrees of freedom. The difference between each emraclidine dose group and placebo at Week 6 will be estimated based on the Least Squares Mean (LSMean) difference between the treatment groups at Week 6 from the MMRM with the associated 95% confidence interval (CI) and P-value. A Cohen's D value will be derived as the ratio of the estimated difference to the population standard deviation at each visit estimated from the model (the square root of the diagonal elements of the estimated covariance matrix). The missing values are assumed to be missing at random for the main analysis, including missing due to missed visits or early termination due to COVID-19 control measures. The LSM ( $\pm$ SE) from the model will be plotted for change in PANSS total score by visit and treatment group. Similarly, the mean ( $\pm$ SD) of absolute values and change from Baseline PANSS total score will be presented by visit and treatment group.

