### Considerations of Data Potentially Missing Not at Random (MNAR)

A pattern mixture model (PMM) approach will be used to address potential MNAR patterns. The following three patterns of subjects in the mITT set will be considered:

1. Subjects with no missing values from discontinuation or from initiation of prohibited concomitant medication during treatment period (No missing)
2. Subjects with missing values from the types of ICEs below will be considered having MNAR:
  - a. Subjects who discontinue due to reasons, as recorded on the eCRF, of lack of efficacy, adverse events related to schizophrenia defined by AEHLGT of Schizophrenia and other psychotic disorders, physician decision, and withdrawal by subject
  - b. Subjects who initiated concomitant prohibited medications (ATC classifications of BUTYROPHENONE DERIVATIVES, INDOLE DERIVATIVES, and OTHER ANTIPSYCHOTICS) after the first dose of IMP and prior to the last dose of IMP with use duration of use of at least 4 days will be considered having a potential confounding ICE. The efficacy data post the start of ICE will be treated as missing with the missing pattern of MNAR.

The MNAR cases will be identified and documented prior to database lock and unblinding ([Section 9.5](#)).

3. Subjects with missing values from the type of ICEs below will be considered as having MAR
  - a. Missing values after discontinuation due to reasons, as recorded on the eCRF, of death, pregnancy, loss to follow-up, adverse event unrelated to schizophrenia, non-compliance, site termination, and COVID-19 control measures will be considered as MAR.

The missing data with MNAR pattern #2 above in the active treatment groups will be imputed tipping point analysis. A set of shift parameters to encapsulate the change in efficacy associated with MNAR due to ICEs for each of the active treatment groups will be applied in the tipping point multiple imputation analysis as described in [Ratitch et al. \(2013\)](#). It is noted, however, MNAR in the placebo group will be imputed as MAR using the standard multiple imputation method.

The MAR pattern #3 above will be imputed using the standard multiple imputation method described above.

Other missing values due to missed visits/assessments before endpoint or discontinuation will also be assumed as MAR and imputed using the standard multiple imputation method for all three patterns.

Core codes for MAR and MNAR imputations are provided in [Section 9.6](#).

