### **5.10.3. Sensitivity Analyses**

The sensitivity analyses described in [Section 5.9.3](#) for the primary estimand will also be performed for the key secondary efficacy estimand.

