## 9.6. Core Codes for Imputation of MAR and MNAR

### 9.6.1. Imputation of Missing at Random (MAR) Cases

SAS PROC MI will be used to generate 25 possible imputed datasets using the following SAS code:

```
proc mi data=mcmc1 seed=SEED1 nimpute=25 out=Out1X;
mcmc chain=multiple displayinit initial=em(itprint);
var TRT Y0 Y1 Y2 ... Yn;
run;
```

Here, TRT is an indicator variable representing treatment with values of 'Emraclidine' or 'Placebo', Y1 - YN are variables representing the response variable (e.g., PANSS total score or CGI-S severity score) for each visit, Y0 is the baseline score, and SEED1 is a random number.

Each of these datasets will be analyzed using PROC MIXED in SAS using the MMRM model. The results of the analyses of the datasets will be combined using PROC MIANALYZE to produce an inferential result.

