### 9.6.2. Imputation of Missing Not at Random (MNAR) Cases

The MNAR cases will be imputed using a tipping point analysis. Subjects identified in [Section 9.5](#) who were treated with values of 'Emraclidine' will have their imputed values that occurred following an ICE shifted by delta. Delta will be defined based on a percentage (10%-90%) of the mixed effect repeated measures model least-square means difference estimate at each visit relative to each 'Emraclidine' arm from the primary endpoint analysis.

First, the SAS code in [Section 9.6.1](#) will be used to generate 25 possible imputed datasets using PROC MI. Then, the delta shift will be applied to these imputed datasets using the code below:

```
data ShiftX;
set Out1X;
if CRIT1FL = 'Y' and DCSRELFL = 'Y' and TRT ^= 'Placebo' then do;
  if AVISITN > VISITN then do;
    AVAL = AVAL0 + DELTA;
    if AVAL > MAX then AVAL = MAX
    if missing < AVAL < MIN then aval = MIN;
    if ABLFL ^= 'Y' then CHG = AVAL - BASE;
  end;
run;
```

Here, TRT is an indicator variable representing treatment with values of 'Placebo' excluded from the delta adjustment, CRIT1FL is an indicator variable representing imputed records with values

of 'Y' indicating a record was imputed, DCSRELEF is an indicator variable representing type of missingness with values of 'Y' indicating an MNAR case, AVISITN is a variable representing the analysis visit, VISITN is a variable representing the subject's last visit prior to the ICE, AVAL0 is a variable representing the original imputed value for the response variable (e.g., PANSS total score or CGI-S severity score) prior to the delta shift, DELTA is a variable representing the shift applied to each imputed value for subjects with treatment values of 'Emraclidine' that occurred after a subject's ICE, AVAL is a variable representing the new value for the response variable following the delta shift, MAX is a variable representing the maximum possible value for the response variable (e.g., 210 for PANSS total score), MIN is a variable representing the minimum possible value for the response variable (e.g., 30 for PANSS total score), ABLFL is an indicator variable flagging the visit that represents the subject's baseline value, BASE is a variable representing the baseline value for the response variable, and CHG is a variable representing the new calculated response variable based on BASE and AVAL.

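### The multiple-imputation code gives both emraclidine doses one treatment coefficient, so if the doses differ the MI and tipping-point analyses pull the two dose contrasts together

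*SAP*

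**What the plan says.** SAP 9.6.1 gives the imputation code. The variable list is "var TRT Y0 Y1 Y2 ... Yn", and the accompanying text says that "TRT is an indicator variable representing treatment with values of 'Emraclidine' or 'Placebo". There is no BY statement and no dose variable. "SAS PROC MI will be used to generate 25 possible imputed datasets" with this code.

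The rest of the plan keeps the doses apart:

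- SAP 5.9.2, the analysis model: "The difference between each emraclidine dose group and placebo at Week 6 will be estimated".
- SAP 5.9.3.2, the shift parameters: they are set "for each of the active treatment groups will be applied in the tipping point multiple imputation analysis".
- SAP 9.6.2: delta is 10% to 90% of the MMRM difference at each visit, "relative to each 'Emraclidine' arm from the primary endpoint analysis". It is added to datasets produced by the 9.6.1 code.
- SAP 5.10.3: the sensitivity analyses "for the primary estimand will also be performed for the key secondary efficacy estimand", so CGI-S uses the same imputation step.

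**The concern.** An imputation model should be at least as rich as the analysis that follows it. Here the analysis has three arms and the imputation has two. A participant's own baseline and earlier scores carry some dose information into each imputed value, but the remaining treatment term is an average over 15 mg and 30 mg. Missing values in the weaker arm are imputed too favourably and those in the stronger arm not favourably enough.

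These analyses exist to show how far each dose's result depends on missing data. With a shared coefficient, the weaker dose's tipping point looks sturdier than it is. A gap between the MI result and the MMRM could also be read as sensitivity to missing data when it comes from the imputation model. A dose difference is a realistic prospect: Protocol 4.3 states that "The 15 mg QD dose is selected to understand the efficacy at a lower dose".

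**Working it through.** **Inputs from the documents.** 1:1:1 allocation with 124 per arm; 25% discontinuation; a difference of 8 points with SD 16.7, or 7 points with SD 14.6; effect size 0.48; 90% power; two-sided alpha 0.05; 25 imputations; delta 10% to 90%.

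**Assumed, because the documents give no figure.** True effect of each dose, correlation between visits, speed of onset, and timing of dropout.

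**The plan's own sample size.** 8/16.7 and 7/14.6 both give 0.48. n = 2(1.960 + 1.282)²/0.48² = 91.2, so 92 per arm. Power at 93 is 90.5% (normal) or 90.3% (t). 93/0.75 = 124, and 3 × 124 = 372. The design reproduces, so its SD and dropout rate are used below. The SAP gives no figure for the imputation step itself.

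**Rough ceiling by hand.** Suppose earlier scores carried no dose information. The shared term would then sit midway between the doses, and the shift in each contrast would be (fraction missing) × (dose difference)/2:

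- Effects 8 and 4: 0.25 × 4/2 = 0.50 points.
- Effects 8 and 0: 0.25 × 8/2 = 1.00 point.
- Effects 8 and 8: 0.

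Earlier scores do carry dose information, so the actual shift should be smaller.

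**Large-sample simulation.** Three arms of 200,000, baseline plus six visits, Week 6 SD 16.7, 25% monotone non-informative dropout, linear onset. Imputation was by sequential normal regression, followed by a baseline-adjusted Week 6 contrast (ANCOVA in place of the MMRM). Entries are 15 mg / 30 mg minus placebo; negative favours emraclidine.

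| True effects | Correlation | Shared term | Dose-specific terms | Shift |
|---|---|---|---|---|
| -4 / -8 | AR(1) 0.6 | -4.31 / -7.51 | -3.91 / -7.91 | 0.40 / 0.40 |
| -4 / -8 | AR(1) 0.8 | -4.39 / -7.79 | -4.06 / -8.12 | 0.33 / 0.33 |
| -4 / -8 | AR(1) 0.9 | -4.24 / -7.71 | -3.97 / -7.97 | 0.27 / 0.26 |
| 0 / -8 | AR(1) 0.6 | -0.74 / -7.15 | 0.05 / -7.94 | 0.79 / 0.79 |
| 0 / -8 | AR(1) 0.8 | -0.59 / -7.38 | 0.05 / -8.02 | 0.64 / 0.64 |
| 0 / -8 | AR(1) 0.9 | -0.48 / -7.46 | 0.04 / -7.97 | 0.52 / 0.51 |
| -8 / -8 | AR(1) 0.8 | -7.94 / -7.96 | -7.93 / -7.96 | 0.01 / 0.00 |

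If the effect instead plateaus by Week 3, earlier visits carry more dose information and the shift falls, at the lowest to 0.09 (effects 4 and 8) and 0.16 (0 and 8), both with AR(1) 0.9. At 35% dropout it rises: with effects 4 and 8, AR(1) 0.6 and linear onset, it is 4.53 - 3.97 = 0.56.

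**Wider grid.** Sixty settings (AR(1) 0.7 to 0.9 or exchangeable 0.5 to 0.7, three onset shapes, two dropout timings, MCAR or MAR), 40,000 per arm:

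| SD | Effects 30 mg / 15 mg | 30 mg understated | 15 mg overstated |
|---|---|---|---|
| 16.7 | 8 / 4 | 0.14 to 0.46 (median 0.34) | 0.16 to 0.46 (median 0.35) |
| 16.7 | 8 / 0 | 0.25 to 0.86 (median 0.66) | 0.32 to 0.90 (median 0.68) |
| 14.6 | 7 / 3.5 | 0.12 to 0.41 | 0.12 to 0.41 |
| 14.6 | 7 / 0 | 0.23 to 0.81 | 0.23 to 0.81 |

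**Trial-size check.** 124 per arm, 25 imputations, Rubin's rules, 100 replicates, AR(1) 0.8. With true effects 0 / -8 the shared term gives -0.67 / -7.16 and dose-specific terms give -0.09 / -7.76. With -4 / -8 the results are -4.39 / -7.64 and -4.05 / -7.96. The standard error is about 2.3 throughout.

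**Tipping-point scale.** If all 25% missing are treated as MNAR, one 10% step moves the Week 6 contrast by 0.25 × 0.10 × effect: 0.10 points at an effect of 4 and 0.20 at 8. The full 90% delta moves the 15 mg contrast by 0.25 × 0.90 × 4 = 0.90. On the wider grid at 8 and 4, 15 mg therefore looks 0.16/0.10 to 0.46/0.10 = 1.6 to 4.6 steps sturdier, which is 18% to 51% of the whole range. The 30 mg dose looks 0.14/0.20 to 0.46/0.20 = 0.7 to 2.3 steps weaker. The early-plateau case above would give 0.09/0.10 = 0.9 steps for 15 mg.

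**Does the per-arm delta remove the pull?** With true effects -4 / -8 and an adverse delta on all missing active-arm Week 6 values:

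| Delta | Shared term | Dose-specific terms |
|---|---|---|
| 10% | -4.25 / -7.49 | -3.92 / -7.81 |
| 50% | -3.77 / -6.72 | -3.44 / -7.05 |
| 90% | -3.36 / -5.82 | -3.04 / -6.14 |

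It does not: the same shift of about 0.3 points appears at every step.

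**The case against.** The best counter-argument is that the appendix is illustrative. The code cannot run as printed: a character TRT cannot sit in an MCMC variable list, 9.6.2 lacks a semicolon and leaves a block unclosed, and the input dataset is not defined. A programmer must recode TRT in any case, and SAP 5.1 defines treatment group as three arms. If each run held one dose plus placebo, or the label were shorthand for the dose arms, the problem would not arise.

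The text does not support those readings. SAP 5.9.3.2 applies the MCMC step to the mITT set, which holds all arms, and sends each imputed dataset to the MMRM with both dose contrasts. SAP 9.6.2 refers to each arm when it means arms, whereas 9.6.1 lists two values. A single numeric variable with three codes would not be enough either, because it would force the treatment term to be linear in the code.

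The size argument does stand. The median shift at 8 and 4 is 0.34/2.4, about 0.14 standard errors. In 300 simulated trials per setting, shared and dose-specific imputation gave different significance verdicts (15 mg / 30 mg) in 3.0% / 0.7% at effects 4 and 8, 2.3% / 4.7% at 0 and 8, and 6.7% / 2.3% at 6 and 8. With equal effects of 8, where there is no bias, the figures were still 1.7% / 2.0%. A 4-point effect averages 4/2.4 = 1.7 standard errors, so at 8 and 4 the average trial has no significant 15 mg result to tip. For the stronger dose the pull is conservative. The step counts also look large partly because the delta grid is narrow.

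**Conclusion.** The concern holds: the imputation rule as written is wrong for a three-arm analysis. When the doses differ, it biases two pre-specified sensitivity analyses of PANSS, in a known direction. CGI-S uses the same step, but the shift there was not quantified. At 25% dropout and SD 16.7, each PANSS contrast moves about 0.1 to 0.5 points if the effects are 8 and 4, and about 0.2 to 0.9 if they are 8 and 0. These ranges rest on assumed dose effects, correlations, onset and dropout timing. With equal effects, the sample-size planning case, there is no bias. H1 to H4 use the three-arm MMRM without PROC MI and are untouched. The shift will seldom reverse a significance verdict, but it is large relative to the tipping-point grid and flatters the weaker dose. It should be corrected.

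**What to change.** In SAP 9.6.1, replace TRT in the variable list with two numeric 0/1 indicators, one for 15 mg and one for 30 mg, or run PROC MI by randomized arm. State in 9.6.2 that the delta shift is applied to those dose-specific imputations, and that this covers both PANSS and CGI-S. Adding geographic region to the variable list, to match the analysis model, is optional.

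The cost is two lines of code and one sentence in the SAP. No further data are needed. The trial-size simulations show essentially the same standard error with dose indicators as with the shared term, so little or no precision is lost.

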### 9.6.2. Imputation of Missing Not at Random (MNAR) Cases

The MNAR cases will be imputed using a tipping point analysis. Subjects identified in [Section 9.5](#) who were treated with values of 'Emraclidine' will have their imputed values that occurred following an ICE shifted by delta. Delta will be defined based on a percentage (10%-90%) of the mixed effect repeated measures model least-square means difference estimate at each visit relative to each 'Emraclidine' arm from the primary endpoint analysis.

First, the SAS code in [Section 9.6.1](#) will be used to generate 25 possible imputed datasets using PROC MI. Then, the delta shift will be applied to these imputed datasets using the code below:

```
data ShiftX;
set Out1X;
if CRIT1FL = 'Y' and DCSRELFL = 'Y' and TRT ^= 'Placebo' then do;
  if AVISITN > VISITN then do;
    AVAL = AVAL0 + DELTA;
    if AVAL > MAX then AVAL = MAX
    if missing < AVAL < MIN then aval = MIN;
    if ABLFL ^= 'Y' then CHG = AVAL - BASE;
  end;
run;
```

Here, TRT is an indicator variable representing treatment with values of 'Placebo' excluded from the delta adjustment, CRIT1FL is an indicator variable representing imputed records with values

of 'Y' indicating a record was imputed, DCSRELEF is an indicator variable representing type of missingness with values of 'Y' indicating an MNAR case, AVISITN is a variable representing the analysis visit, VISITN is a variable representing the subject's last visit prior to the ICE, AVAL0 is a variable representing the original imputed value for the response variable (e.g., PANSS total score or CGI-S severity score) prior to the delta shift, DELTA is a variable representing the shift applied to each imputed value for subjects with treatment values of 'Emraclidine' that occurred after a subject's ICE, AVAL is a variable representing the new value for the response variable following the delta shift, MAX is a variable representing the maximum possible value for the response variable (e.g., 210 for PANSS total score), MIN is a variable representing the minimum possible value for the response variable (e.g., 30 for PANSS total score), ABLFL is an indicator variable flagging the visit that represents the subject's baseline value, BASE is a variable representing the baseline value for the response variable, and CHG is a variable representing the new calculated response variable based on BASE and AVAL.

Following the delta adjustment, each of these datasets will be analyzed using PROC MIXED in SAS using the MMRM model. The results of the analyses of the datasets will be combined using PROC MIANALYZE to produce an inferential result.

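### The SAP's only MNAR analysis is called a tipping point analysis, but delta stops at 90% of the observed effect, no rule says to continue until significance is lost, and the sign of DELTA is not stated

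*SAP*

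**What the plan says.** SAP 9.6.2 states: "The MNAR cases will be imputed using a tipping point analysis". It then sets the shift: "Delta will be defined based on a percentage (10%-90%) of the mixed effect repeated measures model least-square means difference estimate", taken visit by visit and "relative to each 'Emraclidine' arm from the primary endpoint analysis". The program line is "AVAL = AVAL0 + DELTA", bounded only by the ends of the scale, and the explanation reads "DELTA is a variable representing the shift applied to each imputed value for subjects" in the emraclidine arms after the intercurrent event. Neither place gives a sign.

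The main text on MNAR data (SAP 5.9.3.2) says that shift parameters for the active arms "will be applied in the tipping point multiple imputation analysis as described in" a published methods paper. It describes them only as capturing a change in efficacy. It adds that "MNAR in the placebo group will be imputed as MAR using the standard multiple imputation method", so only active-arm records are shifted.

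The other missing-data analyses in SAP 5.9.3.2 are multiple imputation under MAR and an endpoint-completer analysis under MCAR. The summary in SAP 5.11 lists no further MNAR analysis. SAP 5.10.3 repeats the set for CGI-S. Protocol 9.3.2 promises a pattern mixture model with varying shifts by delta adjustment and leaves the details to the SAP.

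**The concern.** A tipping point analysis exists to report the shift at which the conclusion changes, so that readers can judge whether a shift of that size is plausible. A grid that ends at a fixed share of the observed effect does this only when the result happens to tip inside it. When few values are shifted, even the largest shift moves the estimate little, and the report will often be that no tipping point was found. Under the name used in the SAP, that can be taken for robustness without a limit, when it was tested only up to 90%.

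The sign is a second gap in the same specification. Higher PANSS and CGI-S scores are worse. SAP 5.9.2 says "The difference between each emraclidine dose group and placebo at Week 6 will be estimated" but gives no order of subtraction. If the estimate is emraclidine minus placebo, a benefit is negative, and adding a percentage of it to an imputed score improves that score.

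**Working it through.** **Inputs.** Two-sided alpha is 0.05 (SAP 5.3). SAP 1.2 gives 93 completers per arm, effect size 0.48 (7 points with SD 14.6, or 8 with SD 16.7), at least 90% power, 25% discontinuation and 372 randomized. The largest multiple is k = 0.9 (SAP 9.6.2).

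**The plan's own figures.** A normal-approximation calculation for effect 0.48 and 90% power gives 92 per arm, against 93 stated. Power with 93 is 0.905. 93/0.75 = 124, and 3 × 124 = 372. The design reproduces.

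**Assumption.** f, the share of active-arm Week 6 values that are shifted, is not in the documents available. 25% corresponds to every planned discontinuation being classed as MNAR. The MNAR reasons are only a subset of discontinuations, but users of prohibited antipsychotics are added, so f could fall on either side. I show 15% and 25%.

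**Effect of the shift, taken as a worsening.** Moving a fraction f by k times the observed difference D changes the estimate to D(1 − fk), with the standard error nearly unchanged (1.004 to 1.010 times the unshifted value in simulation). At k = 0.9 a result tips only if its z is below 1.96/(1 − 0.9f):

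- f = 15%: 1.96/0.865 = 2.27, p = 0.0235
- f = 25%: 1.96/0.775 = 2.53, p = 0.011

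**Share of significant results that can tip.** With z ~ N(m, 1) and m = effect × √(93/2), the share is P(1.96 < z < limit)/P(z > 1.96):

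| True effect (SD) | m | f = 15% | f = 25% |
|---|---|---|---|
| 0.48 | 3.27 | 7% | 15% |
| 0.40 | 2.73 | 13% | 26% |
| 0.30 | 2.05 | 23% | 41% |
| 0.25 | 1.70 | 28% | 49% |

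At f = 25% the share reaches one half at an effect of about 0.24, and at 0.20 it is 56%.

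**A result at the design z.** With f = 25%, 3.273 × 0.775 = 2.54, so p = 0.011 after the 90% shift. The multiple needed to tip is (1 − 1.96/3.273)/0.25 = 1.60, which is 11.2 points if D = 7. The grid ends at 0.9 × 7 = 6.3 points.

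**Simulation check.** The settings were 124 per arm, SD 14.6, 25 imputations, Rubin's rules, an assumed correlation of 0.7 between an earlier visit and Week 6, and 1,500 runs per setting. The share of significant results that tipped at f = 15% and 25% was 5% and 13% (D = 7), 15% and 31% (D = 5), and 26% and 50% (D = 3.5, which is 0.24 SD). This agrees with the formula.

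**Opposite sign.** At f = 25% the design z becomes 3.273 × 1.225 = 4.01. In the simulation, no significant result was weakened.

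**The case against.** The strongest reply is that this is largely a matter of naming. The protocol never promises a tipping point, only varying shifts by delta adjustment, and a 10%–90% grid delivers that. With few shifted values, surviving the grid correctly reflects limited missing data. A shift of 100% already removes roughly the whole observed benefit from each shifted participant while placebo stays at MAR, so going further supposes that these participants did worse than losing all benefit. The cited methods paper may also contain a search rule.

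Much of this stands: surviving the grid is real evidence, and where to stop is a judgement. But it is the SAP that uses the name, and its grid would often not deliver what the name promises. A general citation, which could not be checked here, would not displace an explicit range.

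Three stronger readings are tempting and not supported.

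- A reader might infer that the plan shifts scores in the drug's favour. The documents leave the sign open. Shifting only the active arm makes sense as a worsening, and the phrase "relative to each 'Emraclidine' arm from the primary endpoint analysis" can be read as placebo minus emraclidine.
- A reader might infer that the grid can hardly ever tip. It can expose results near the significance limit, which are the ones most in need of testing, and it tips more often as f rises. I give no shares above 25%, because holding 93 completers fixed would then understate tipping.
- A reader might use the phase 1b results in Protocol 2.2.3 to argue that shifts well above 90% are plausible. Those results are arm averages from 27 participants on 30 mg. The imputations here use each participant's own earlier scores, so those who left doing poorly already have worse imputed values.

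**Conclusion.** The point holds in bounded form. As written, SAP 9.6.2 describes a delta-adjustment analysis with a ceiling, not a search for a tipping point, and its sign needs to be stated. For true effects of 0.25 to 0.48 SD and f of 25% or less, more than half of significant results would show no tipping point. At f = 25% and effects below about 0.24 SD, that majority claim fails. These figures rest on an assumed f, the planned 93 completers, a worsening shift and a nearly constant standard error. The 90% cap, the absence of a stopping rule and the missing sign depend on none of these. The matter should be fixed, but it concerns a sensitivity analysis and leaves the primary test unaffected.

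**What to change.** State that DELTA is a worsening, positive on both PANSS and CGI-S, for example k times the absolute LS-mean difference. Run k from 0 in fixed steps past 100%, until each dose's Week 6 comparison loses significance or a plausibility limit set before unblinding is reached. Report the tipping delta in scale points beside the observed effect, or report that none was found up to that limit.

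If the 10%–90% grid is kept, call it a bounded delta-adjustment analysis and still state the sign.

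The cost is a change of SAP wording and a few more program runs. The team must justify a plausibility limit in advance, and the reported robustness may look less favourable.
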